APPENDIX B: CLINICAL LABORATORY ANALYTES

Standard Safety Chemistry Panel

Alanine aminotransferase	Albumin
Alkaline phosphatase	Amylase
Aspartate aminotransferase	Bicarbonate
Blood urea nitrogen	Calcium
Chloride	Creatine kinase
	Estimated glomerular filtration rate (eGFR)
Creatinine	[1]
Gamma-glutamyl transferase	Glucose
Inorganic phosphorus	Lactate dehydrogenase
Lipase	Potassium
Sodium	Total bilirubin
Total protein	Uric acid

1. Calculated by the central laboratory using the Chronic Kidney Disease Epidemiology Collaboration (CKD-EPI) formula for patients ≥ 18 years of age and the revised bedside Schwartz formula for patients 12 to 17 years of age:

$$eGFR = 141 \times \min(SCr/K, 1)^{\alpha} \times \max(SCr/K, 1)^{-1.209} \times 0.993^{Age} \times 1.018[\text{if female}] \times 1.159[\text{if black}]$$
where SCr is standardized serum creatinine in mg/dL, K is 0.7 for females and 0.9 for males, α is -0.329 for females and -0.411 for males, min indicates the minimum of SCr/K or 1, and max indicates the maximum of SCr/K or 1).
Reference: Levey AS, Stevens LA, Schmid CH, et al. A new equation to estimate glomerular filtration rate. *Ann Intern Med.* 2009;150(9):604-612.
Bedside Schwartz formula = $([0.413 \times \text{height (cm)}] / \text{Scr [mg/dL]})$.

Serology

Hepatitis B virus	Hepatitis C virus
Human immunodeficiency virus	

Coagulation

International normalized ratio (INR) [1]

1. INR testing is to be completed as part of Screening assessments only (Visit 1 or Visit 2). Thereafter, INR will be tested as part of follow-up assessments for a suspected case of drug-induced liver injury (DILI). See [Appendix C](#) for details regarding additional follow-up assessments to be completed for suspected cases of DILI.

Endocrinology

Follicle-stimulating hormone (FSH) [1]	Human chorionic gonadotropin [2]
Thyroid-stimulating hormone	Thyroxine (T4)

1. In female patients who are not using hormonal contraception or hormonal replacement therapy but with suspected menopause and less than 12 months of amenorrhea, a high FSH level in the postmenopausal range will be required at Screening to confirm a postmenopausal state.
2. For women of childbearing potential only. A serum pregnancy test will be performed at Study Visit 2. A pregnancy test via a local urine assessment will be performed at all other applicable study visits prior to study drug dosing.

Hematology

Hematocrit

Platelets

Reticulocyte count

Hemoglobin

Red blood cell count

White blood cell count and differential [1]

1. Manual microscopic review is performed only if white blood cell count and/or differential values are out of reference range.

Urinalysis (Freshly Voided Urine)

Assessed by Dipstick

Bilirubin

Glucose

Leukocyte esterase

pH

Specific gravity

Blood

Ketones

Nitrite

Protein

Urobilinogen

Assessed by Chemical Assay

Albumin

Creatinine

Sodium

Cortisol

Protein

Urine Drug Screen (Freshly Voided Urine)

Alcohol

Cannabinoids

Ecstasy

Opiates

Amphetamines

Cocaine

Methamphetamine

Oxycodone

24-Hour Urine Analysis

Creatinine clearance

Total cortisol

Total protein

Total albumin

Total creatinine

Urine protein to creatinine ratio (UPCR)

Exploratory Biomarkers

Urine-Based Biomarkers

B2-M

EGF

MCP-1/Cr

Osteopontin

Cystatin-C

KIM-1

NGAL

TGF- β 1

Serum-Based Biomarkers

B2-M	BUN
CCL3	Cystatin-C
IL1B	MCP-1
TGF-β1	TIMP1
TNFα	VEGF
YKL-40	

Plasma-Based Biomarkers

CCN2	MMP9
NGAL	SPP1

APPENDIX C: DETECTION AND MANAGEMENT OF SUSPECTED OR CONFIRMED CASES OF DRUG-INDUCED LIVER INJURY

Particular attention will be given to the detection and management of suspected or confirmed cases of drug-induced liver injury (DILI). If any of the following laboratory results or clinical signs or symptoms are obtained during the study, the Investigator will instruct the patient to return to the study center within 48 hours of receipt of the laboratory test results to undergo a retest:

- Aspartate aminotransferase (AST) or alanine aminotransferase (ALT) $\geq 3 \times$ the upper limit of normal (ULN);
- AST or ALT $> 2 \times$ Baseline;
- Total bilirubin $> 2 \times$ ULN; or
- Clinical signs or symptoms that are, in the opinion of the Investigator, consistent with hepatitis (such as right upper quadrant discomfort, fever, fatigue, nausea, vomiting, jaundice, rash, or eosinophilia $> 5\%$) or drug-induced hepatotoxicity. Isolated eosinophilia $> 5\%$ without clinical signs or symptoms that are consistent with hepatitis or hepatotoxicity by the Investigator's medical judgment, should not be considered suspected DILI. Retesting of eosinophilia ($> 5\%$) will only be required in case this is observed in combination with at least 1 of the other criteria listed above.

Baseline values for liver tests (ALT, AST, and total bilirubin) are determined by averaging the values obtained at Screening Visits 1 and 2 to obtain the arithmetic mean.

The results of the test and retest will be reviewed to determine if they meet Criteria 1, 2, or 3, as outlined below.

Criteria for Close Monitoring of Liver Biochemistry and IMP Action

Criteria for close monitoring of liver biochemistry and investigational medicinal product (IMP) action include the following:

1. For patients with **Baseline ALT and/or AST $< \text{ULN}$** , unless an alternative cause for the laboratory abnormalities is immediately apparent in the opinion of the Investigator and documented at the time of the laboratory test elevations, close monitoring for suspected DILI will be performed in patients with any of the following criteria confirmed by repeat testing:
 - a. ALT or AST $> 3 \times$ ULN;
 - b. Total bilirubin $> 2 \times$ ULN;
 - c. International normalized ratio (INR) > 1.5 (except for patients on anticoagulant therapy); or
 - d. Clinical signs or symptoms that are, in the opinion of the Investigator, consistent with hepatitis (such as right upper quadrant discomfort, fever, fatigue, nausea, vomiting, jaundice, rash, or eosinophilia $> 5\%$) provided the latter is in combination with any of the other criteria listed under Criterion 1).
2. For patients with **Baseline ALT and/or AST between $\geq \text{ULN}$ and $< 3 \times \text{ULN}$** , unless an alternative cause for the laboratory abnormalities is immediately apparent in the opinion of the

Investigator and documented at the time of the laboratory test elevations, close observation for suspected DILI will be performed in patients with any of the following criteria confirmed by repeat testing:

- a. ALT or AST $>2 \times$ Baseline at any time;
- b. Total bilirubin $>2 \times$ ULN;
- c. INR >1.5 (except for patients on anticoagulant therapy); or
- d. Clinical signs or symptoms that are, in the opinion of the Investigator, consistent with hepatitis (such as right upper quadrant discomfort, fever, fatigue, nausea, vomiting, jaundice, rash, or eosinophilia $>5\%$ provided the latter is in combination with any of the other criteria listed under [Criterion 2](#)).

During the close monitoring period in [Criteria 1](#) or 2, IMP can be continued, unless any of the following occur:

- The patient is symptomatic in addition to having elevated laboratory parameters;
 - Close monitoring is not possible;
 - Criterion 3 (see below) are met and no other cause for laboratory abnormalities is clinically apparent and documented by the Investigator in the study documents; or
 - At the discretion of the Investigator.
3. **For patients meeting any of the following events**, IMP will be discontinued when no other cause for the laboratory abnormalities is immediately apparent:
- a. ALT or AST $>5 \times$ Baseline;
 - b. ALT or AST $>10 \times$ ULN;
 - c. ALT or AST $>3 \times$ Baseline with 1 or more of the following; or
 - Total bilirubin $>2 \times$ ULN;
 - Total bilirubin $>1.5 \times$ Baseline and $>ULN$;
 - INR >1.5 (except for patients on anticoagulant therapy); or
 - Clinical signs or symptoms that are, in the opinion of the Investigator, consistent with drug-induced hepatotoxicity.
 - d. ALT or AST $>$ Baseline with any 2 or more of the following:
 - Total bilirubin $>2 \times$ ULN or $1.5 \times$ Baseline;
 - INR >1.5 (except for patients on anticoagulant therapy); or
 - Clinical signs or symptoms that are, in the opinion of the Investigator, consistent with drug-induced hepatotoxicity.

If the above criteria in Criterion 3 are met, the Investigator will instruct the patient to discontinue IMP administration and return to the study center within 48 hours of receipt of the laboratory test results to undergo a retest and additional investigations (ie, close monitoring) to assess for suspected DILI. IMP cannot be reintroduced.

Any suspected or confirmed DILI event, defined as events meeting [Criteria 1, 2, or 3](#) above, will be closely monitored by the Investigator and the Independent Data Monitoring Committee.

Close Monitoring Activities

Close monitoring for all patients who meet suspected DILI evaluation Criteria 1, 2, or 3 (laboratory analytes are performed at the central laboratory) includes the following:

- Monitor patient 2 or 3 times weekly until liver biochemistries (ALT, AST, alkaline phosphatase, total bilirubin), and coagulation profile (INR) resolve, stabilize or return to within Baseline values. Additional tests (eg, conjugated bilirubin) should also be obtained, as appropriate, at the discretion of the Investigator; and
- Monitor liver biochemistries and coagulation profile once a week or less according to the Investigator's judgment if the abnormalities stabilize, resolve, or return to within Baseline values, or IMP has been discontinued and the patient is asymptomatic.

Close monitoring can be stopped based on the Investigator's clinical judgment once the abnormalities stabilize, resolve, or return to within Baseline values; or when there is an alternative documented cause to explain the deterioration.

Follow-Up Procedures

Recommended follow-up procedures (per Investigator decision) to exclude alternative causes for suspected DILI (laboratory analyses, as applicable, performed at the local laboratory) include the following:

- Obtain a detailed history for symptoms assessment: appearance or worsening of clinical symptoms of hepatitis (such as right upper quadrant discomfort, fever, fatigue, nausea, vomiting, jaundice, rash, or eosinophilia >5%);

Note: If a patient is symptomatic in addition to having elevated laboratory parameters, the drug must be discontinued immediately, and a suspected DILI evaluation must be performed.

- Obtain a more detailed history of prior or concomitant diseases;
- Obtain a history for concomitant medications, acetaminophen, dietary supplements, herbal remedies, other over the counter medications, recreational drug use, and special diets;
- If possible, quantify the alcohol consumption to assess for alcoholic hepatitis;
- Obtain a history of exposure to environmental chemical agents;
- If INR is also elevated, a trial of intravenous vitamin K administration may be considered, especially in cholestatic patients;
- Viral hepatitis serology, including:
 - Hepatitis A immunoglobulin M (IgM) antibody;
 - Hepatitis B surface antigen and Hepatitis B core antibody (IgM);
 - Hepatitis C RNA;
 - Hepatitis E IgM antibody;

- Cytomegalovirus IgM antibody; and
- Epstein-Barr viral capsid antigen IgM antibody (or if unavailable, obtain heterophile antibody or monospot testing); however, IgM antibodies must be sent out as soon as possible.
- Follow-up on signs and symptoms consistent with potential immune-mediated injury and, if relevant, monitor until the abnormalities resolve and to the End of Study Visit, including the following:
 - Fever, malaise, pruritus, etc;
 - Rash;
 - Edema;
 - Lymphadenopathy;
 - Hematological changes (leukopenia, anemia, thrombocytopenia, etc), urinalysis, electrocardiogram, etc; and
 - Other organ involvement, in addition to liver (kidney, heart, lungs, etc).
- Other laboratory tests and assessments including:
 - Serum creatine phosphokinase and lactate dehydrogenase;
 - Fractionate bilirubin, if total bilirubin $>2 \times$ ULN;
 - A liver biopsy, at the discretion of the Investigator;
 - Assess for peripheral eosinophilia. Investigators are also encouraged to obtain a skin biopsy in patients who have liver enzyme elevation together with eosinophilia; and
 - Assess for hypoxic/ischemic hepatopathy, and biliary tract disease.

In addition, recommendation to undertake the following for patients who meet the stopping criteria for both ALT and total bilirubin **OR** experience clinical symptoms of hepatitis:

- Antinuclear antibody, antismooth muscle antibody, Type 1 anti-liver kidney microsomal antibodies and quantitative total immunoglobulin G (or gamma globulins);
- If required, evaluation of competing undiagnosed liver disease (hemochromatosis, Wilson's disease, alpha-1 anti-trypsin deficiency);
- Serum acetaminophen levels **OR** serum acetaminophen adducts by high performance liquid chromatography assay (quantifies potential acetaminophen contribution to liver injury in patients with definite or likely acetaminophen use in the preceding week); and
- Liver imaging (ultrasound, magnetic resonance, or computerized tomography) to evaluate liver disease at the discretion of the Investigator.

1 INTRODUCTION

The purpose of this Statistical Analysis Plan (SAP) is to provide a description of the statistical methods to be implemented for the analysis of data from the study with protocol number GSN000500. The SAP will be finalized prior to database lock. Any deviations from the SAP after database lock will be documented in the final Clinical Study Report (CSR).

2 STUDY OVERVIEW

2.1 Study Objectives

2.1.1 Primary Objective and Endpoint

Primary	
Objective	Endpoint
To evaluate the safety and tolerability of setanaxib compared to placebo in patients with Alport syndrome.	
 Percentage of patients with treatment-emergent serious adverse events (SAEs); and Percentage of patients with treatment-emergent adverse events of special interest (AESIs), i.e., anemia.

2.1.2 Safety Objectives and Endpoints

Safety	
Objective	Endpoint
To assess the effect of setanaxib on vital signs compared to placebo.	Percentage of patients with clinically significant changes in heart rate and blood pressure.
To evaluate the effect of setanaxib on 12-lead ECGs compared to placebo.	Percentage of patients with clinically significant changes in 12-lead ECG.
To evaluate the effect of setanaxib on physical examinations compared to placebo.	Percentage of patients with clinically significant changes in physical examination.
To evaluate the effect of setanaxib on clinical laboratory parameters compared to placebo.	Percentage of patients with clinically significant changes in hematology, serum chemistry, urinalysis, and thyroid function.
To evaluate the effect of setanaxib on hearing compared to placebo.	Percentage of patients with clinically significant changes in hearing audiometric testing (bone- and air-conduction).

2.1.3 Secondary Objectives and Endpoints

Secondary	
Objective	Endpoint
To assess the effect of setanaxib on urine protein to creatinine ratio (UPCR) compared to placebo.	
 The ratio of UPCR at 24 weeks compared to baseline; and Percentage of patients with a 25% reduction in UPCR at 24 weeks, compared to baseline.
To assess the effect of setanaxib on estimated glomerular filtration rate (eGFR) compared to placebo.	The ratio of eGFR at 24 weeks compared to baseline.
To assess the plasma exposure of setanaxib and its active metabolite GKT138184.	
Pre-dose and post-dose plasma concentrations of setanaxib and GKT138184 at a steady state. The following PK properties will be calculated:
 
 Area under the concentration-time curve over 24 hours at steady state ($AUC_{0-24-ss}$); Minimum plasma concentration at steady state (C_{min-ss}); and Maximum plasma concentration at steady state (C_{max-ss}).

2.1.4 Exploratory Objectives and Endpoint

Exploratory	
Objective	Endpoint
To assess the effect of setanaxib on biomarkers of inflammatory pathways, fibrosis, or disease progression compared to placebo.	
Change from baseline at 24 weeks in the following parameters:
 
Urine-based biomarkers: MCP-1/Cr, EGF, Cystatin-C, TGF-β1, NGAL, KIM-1, B2-M, and osteopontin;
 
Serum-based biomarkers: MCP-1, BUN, Cystatin-C, B2-M, TGF-β1, CCL3, IL1B, TIMP1, TNFα, VEGF, and YKL-40; and
 
Plasma-based biomarkers: NGAL, MMP9, SPP1, and CCN2.

Potential optional future analysis to assess the effect of setanaxib on additional biomarkers of inflammatory pathways, fibrosis, or disease progression compared to placebo.	Where allowed per local regulations, IEC approval and patient consent (and assent, where applicable), optional exploratory blood and urine samples will be collected. The samples will be used to assess additional biomarkers of Alport syndrome, inflammatory

	pathways, fibrosis, or disease progression compared to placebo. This may include, but will not be limited to, ADMA, TIMP-2, IGFBP7, and COL1A1.
--	---

2.2 Study Design

2.2.1 Overview

This is a randomized, double-blind, placebo-controlled Phase 2a study assessing oral setanaxib in patients with Alport syndrome. The safety, tolerability, pharmacokinetics (PK), pharmacodynamics (PD), and preliminary efficacy of setanaxib will be assessed over 24 weeks of treatment. Patients are required to have persistent proteinuria (UPCR ≥ 90 mg/mmol [0.8 g/g]) despite treatment with a stable dose of RAS (Renin-angiotensin system) inhibitor therapy (ACEis and/or ARBs) at the maximum allowed dose or maximum-tolerated daily dose for at least 8 weeks prior to consent/assent. Patients should remain on their regimens of RAS inhibitors for the whole duration of the study.

This study aims to assess the safety of setanaxib as an add-on treatment to current RAS inhibitor treatment, in patients with Alport syndrome at risk of disease progression and with limited treatment options available. The double-blind, placebo-controlled design is chosen to provide safety data and preliminary efficacy for setanaxib in addition to the standard of care treatment in this patient population with a standard of care (with placebo) arm as reference. This will help to guide the design of further Phase 2/3 studies of setanaxib in Alport syndrome.

The study is planned to enroll and treat approximately 18 patients, eligible patients will be randomized in a 2:1 ratio, respectively to the following treatment groups:

- Setanaxib group:
 - For patients aged 12 to 17 years: 1200 mg/day (800mg morning + 400mg evening) for 24 weeks.
 - For patients aged ≥ 18 years: 1600mg/day (800mg twice daily) for 24 weeks.
- Placebo group: matching placebo tablets daily.

Up to 6 patients should be in the age group of 12 to 17 years old at the time of consent/assent, and a minimum of 12 patients should be ≥ 18 years of age. To ensure balance among treatment groups, randomization will be stratified by age group (12 to 17 year of age and ≥ 18 years of age) at the time of consent/assent.

Patients must take the first dose of study drug in the presence of site staff during Study Visit 3 (Day 1). Similarly, the morning dose at the week 2, week 12, and week 24 visit should be taken at the study site, to allow for proper PK sampling.

The estimated study duration for an individual patient is up to approximately 32 weeks. Following a 4-week screening period (Note: the screening period may be longer than 4 weeks, as needed, to complete genetic testing), patients will receive setanaxib or placebo for a 24-week treatment period, followed by a 4-week follow-up period.

Refer to Table 2 Schedule of Procedures in the protocol for a complete list of procedures to be completed at each study visit.

3 STATISTICAL METHODOLOGY

3.1 General Considerations

3.1.1 Analysis Day

Analysis day will be calculated from the date of first dose of study drug. The day of the first dose of study drug will be Day 1, and the day immediately before Day 1 will be Day -1. There will be no Day 0.

3.1.2 Analysis Visits

Scheduled visits will be assigned to analysis visits as recorded on the Case Report Form (CRF). Unscheduled and early termination (ET) visits will be assigned to analysis visits according to the following visit windows:

Analysis Visit	Target Analysis Day	Low Analysis Day	High Analysis Day
Day 1 (Visit 3)	1	NA	NA
Week 2 (Visit 4)	15	2	29
Week 6 (Visit 5)	43	30	64
Week 12 (Visit 6)	85	65	106
Week 18 (Visit 7)	127	107	148
Week 24 (EOT) (Visit 8)	169	149	183
Week 28 (Safety FUP)	197	184	197+

For each analysis visit, if a scheduled visit occurs within the analysis day window, then the measurement from this scheduled visit will be used as the measurement for the analysis visit. If no scheduled visit occurs within the analysis day window, the unscheduled measurement closest to the target day will be used. If measurements are equidistant to the target day, the latter will be used. If no visits occur within the analysis day window, the measurement for this analysis visit will be treated as missing.

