8.8.1 Detection and Management of Potential Bone Marrow Toxicity

Particular attention will be given to the detection and management of potential cases of bone marrow toxicity. In case of Grade ≥ 2 severity anemia, the Investigator will instruct the patient to interrupt IMP administration and to return to the study site within 7 days so that the absolute reticulocyte count can be retested. If the retest value is below 50% of the baseline value (Screening Study Visit 2), IMP will not be resumed and will be permanently discontinued. IMP administration will be resumed only if the retest value of the absolute reticulocyte count is $\geq 50\%$ of the baseline value and a Grade ≤ 1 of anemia, and an alternative cause for the anemia can be documented. The patient will continue to be closely monitored (at least weekly) until normalization of the reticulocyte count, ie, return to baseline values.

Anemia will be reported to the Sponsor (or designee) as an AESI, as defined in [Section 8.1.4](#), following the same procedure as for SAEs ([Section 8.3](#)).

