3.4.1 Adverse Events -Primary Endpoint

The primary endpoints are:

- Percentage of patients with treatment-emergent SAEs;
- Percentage of patients with treatment-emergent AESIs.

All adverse events (AEs) will be coded to SOC and PT using MedDRA version v 26.1. Treatment-emergent adverse events (TEAEs) are defined as AEs that start after the first dose of study drug and up to 30 days post-last dose of study drug. Pre-treatment AEs are defined as AEs that started prior the first dose of study drug and post-treatment AEs are defined AEs that started more than 30 days after last dose of study drug.

AESI is defined as CTCAE Grade ≥ 2 anemia, defined as hemoglobin <10g/dL, and absolute reticulocyte counts of <50% of the baseline value (Screening Study Visit 2), which are confirmed by repeat testing.

Estimand

To assess the primary endpoint for treatment-emergent SAE, the safety estimand is defined by the following key attributes, according to the framework provided in International council for Harmonization (ICH) E9 (R1) [1]:

- **Treatment:** Setanaxib treated patients compared to placebo
- **Population:** The SAS comprised of all randomized patients who took at least 1 dose of the study drug.
- **Variable of interest:** Treatment-emergent SAEs
- **Intercurrent event handling:** All events will be counted regardless of early discontinuation of treatment, up to 30 days post-last dose of study drug
- **Summary measures:** Count and percentage of patients experiencing SAEs during the Treatment Period up to 30 days post-final dose.

The number and percentage of patients with SAEs will be presented by treatment group, system organ class (SOC), and preferred term (PT). Similar summaries will be presented for treatment emergent AESIs. The number and percentage of patients with study drug related treatment-emergent SAEs and AESIs will be presented by treatment group, SOC and PT.

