3.4.3 Clinical Laboratory Tests

Clinical laboratory evaluations (including serum chemistry, hematology, endocrinology/thyroid function, and urinalysis) will be obtained as indicated in Table 2 Schedule of Procedures in the protocol and processed by a central laboratory. A list of laboratory tests to be performed are included in Appendix B in the protocol.

Laboratory values and changes from baseline will be presented at each visit and baseline by laboratory test. In addition, the number and percentage of patients with parameters outside the normal range (below the lower limit of normal ($<LLN$) or above the upper limit of normal ($>ULN$)) will be presented by visit and treatment group. The count and percentage of patients with clinically significant changes will be tabulated by treatment group. Clinically significant changes will be identified as any TEAEs related to significant change in laboratory test. Medical review of AE will be performed by Medpace to identify any clinically significant changes. The provided classifications will be used in analysis.

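### By-visit laboratory tables leave out toxicity retests whenever the scheduled visit was attended, and no worst post-baseline summary is planned

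*SAP*

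**What the plan says.** **Selection of values.** SAP 3.1.2 assigns unscheduled and early-termination visits to analysis visits by day window. Within a window, "if a scheduled visit occurs within the analysis day window, then the measurement from this scheduled visit will be used". The exception is: "If no scheduled visit occurs within the analysis day window, the unscheduled measurement closest to the target day will be used".

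**Laboratory tables.** SAP 3.4.3 states: "Laboratory values and changes from baseline will be presented at each visit and baseline by laboratory test". Counts below the lower or above the upper limit of normal "will be presented by visit and treatment group". It names no worst post-baseline, shift, grade or liver-threshold table. One further table does not depend on the windows: "Clinically significant changes will be identified as any TEAEs related to significant change in laboratory test".

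**Retests.** Protocol 8.8.1 brings a patient with Grade 2 or higher anaemia back within 7 days for a reticulocyte retest, and then: "The patient will continue to be closely monitored (at least weekly) until normalization of the reticulocyte count". Appendix C calls for a liver retest within 48 hours of receipt of the results. If the monitoring criteria are met, it continues: "Monitor patient 2 or 3 times weekly until liver biochemistries".

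**AESI.** SAP 3.4.1 defines the only AESI as haemoglobin below 10 g/dL together with reticulocytes below 50% of baseline, "which are confirmed by repeat testing".

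**Listings.** SAP 7 puts all available data into patient listings.

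**The concern.** Marrow toxicity and liver injury are the two laboratory harms for which the protocol lays down its own retest schedule. Those extra samples are drawn because toxicity is suspected. The selection rule then sets them aside in favour of the scheduled value.

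The primary objective is safety. A reader comparing arms on haemoglobin, reticulocytes or transaminases would use the SAP 3.4.3 tables, and their per-visit minimum and maximum would not show how far a value fell or rose between visits. After Grade 2 or higher anaemia the study drug is interrupted (Protocol 8.8.1), so the next scheduled value may be off drug. Protocol 4.3 encourages patients who stop study drug to keep attending, so their scheduled visits go on taking precedence.

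**Working it through.** **1. Reproduce the windows.** Target days in SAP 3.1.2 are 15, 43, 85, 127, 169 and 197. Each upper limit is the midpoint of adjacent targets:
- (15+43)/2 = 29
- (43+85)/2 = 64
- (85+127)/2 = 106
- (127+169)/2 = 148
- (169+197)/2 = 183

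All five agree with the SAP. Each window starts the day after the previous one ends (30, 65, 107, 149, 184), so there is no gap from Day 2 onward.

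**2. Place the retests.** The Schedule of Procedures allows ±3 days at Week 2 and ±7 days at the later visits. Take the latest allowed visit day and add 2 days (liver) or 7 days (marrow). This assumes both delays run from the visit day.

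| Visit | Latest day | +2 | +7 | Window limit |
|---|---|---|---|---|
| Week 2 | 18 | 20 | 25 | 29 |
| Week 6 | 50 | 52 | 57 | 64 |
| Week 12 | 92 | 94 | 99 | 106 |
| Week 18 | 134 | 136 | 141 | 148 |
| Week 24 | 176 | 178 | 183 | 183 |

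Every first retest falls in the window of the visit that triggered it. The 48 hours actually runs from receipt of results, so laboratory turnaround adds to the +2. The slack from the latest visit day is 11 days at Week 2, 14 at Weeks 6, 12 and 18, and 7 at Week 24. A late Week 24 retest could move to the Week 28 window, where an attended follow-up visit would displace it.

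**3. Follow the later samples.** Because the windows are contiguous, each further weekly or twice- to thrice-weekly sample also shares a window with a scheduled visit. As an illustration, three weeks of liver monitoring gives 2×3 = 6 to 3×3 = 9 values. If all scheduled visits are attended, none enters a by-visit table.

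**4. Early termination.** Suppose Week 6 was attended on Day 43 and the patient leaves on Day 60. Day 60 lies in window 30–64, which already holds a scheduled visit, so the early-termination value is not selected. This assumes early-termination visits do not count as scheduled. SAP 3.1.2 groups them with unscheduled visits for window assignment.

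**5. When would an out-of-range count change?** ALT at or above 3×ULN at a scheduled visit is already above ULN. Haemoglobin below 10 g/dL would ordinarily be below the lower limit. A worse retest leaves those counts unchanged. A count changes only if the parameter is in range at the scheduled visit and out of range only at a retest or early-termination visit. This could happen for reticulocytes. It could also happen under the trigger of ALT or AST above 2×baseline: with an assumed baseline of 0.4×ULN, a scheduled 0.9×ULN is 2.25×baseline, yet in range.

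**6. Scale.** About 18 patients at 2:1 gives 12 and 6. One patient is 1/12 = 8.3 points on setanaxib or 1/6 = 16.7 points on placebo. These figures apply only in the situation of step 5, or in a threshold row that the SAP does not now have.

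**The case against.** A reader might infer that the retests enter no safety table and reach listings only. The documents do not support that:
- The retest decides whether a patient counts in the AESI table, which is a primary endpoint.
- The table of clinically significant laboratory changes is built from TEAEs after medical review, outside the windows.
- SAP 3.4.2 tabulates TEAEs by maximum severity, at Grade 3 or higher, and leading to discontinuation.
- Protocol 8.1 says abnormalities that require action with study drug should usually be reported as AEs. Grade 2 or higher anaemia and Appendix C Criterion 3 both require such action.

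The rest of the case against also has weight. Choosing one value per visit is ordinary practice for by-visit summaries. An unscheduled value is used when its window holds no scheduled visit, and a nadir or peak on a scheduled day appears in that visit's minimum or maximum. Nothing in the documents shows that the worst value will fall at a retest; Protocol 1.3.2 reports that affected dogs, one excepted, tended to recover when dosing was reduced or stopped. With about 18 patients, listings are readable, and an unblinded IDMC reviews safety.

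All of this stands, but it leaves a gap. Liver injury is not an AESI. An isolated fall in haemoglobin or reticulocytes is not one either, because both criteria are required. Whether a laboratory abnormality becomes an AE depends partly on investigator judgement. AE tables give events and severity grades, not the depth of a nadir or the height of a peak.

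**Conclusion.** The point holds, limited to the numeric laboratory tables. When scheduled visits are attended, retest values do not enter them. An early-termination value can be displaced in the same way, and no worst post-baseline summary makes up for it. An extreme found only at such a visit is visible by arm through AE and AESI coding alone, and otherwise in listings. The loss is mainly in how severe an abnormality became, less often in whether it occurred.

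Its size cannot be computed. It is tempting to count the untabulated samples, but that does not measure bias: monitoring may be reduced or ended once values stabilise or resolve. The 8.3-point figure is likewise the weight of one patient, not an expected error. No problem is shown for TSH, free T4 or QTcF; the protocol sets out no comparable retest series for them, and the QTcF threshold summary in SAP 3.4.5 is not stated to be by visit.

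The conclusion assumes that scheduled visits are attended within their protocol windows and that the SAP text lists all planned laboratory tables. This is a worthwhile, inexpensive improvement to a descriptive study whose primary objective is safety. It contradicts nothing in the protocol.

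**What to change.** In SAP 3.1.2, state that the visit windows govern by-visit summaries only.

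In SAP 3.4.3, add a by-arm worst post-baseline summary with a shift from baseline, covering:
- minimum haemoglobin and minimum reticulocyte count, each also as a percentage of baseline;
- maximum ALT, AST and total bilirubin.

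Use all scheduled, unscheduled and early-termination values from first dose to 30 days after last dose, to match the TEAE period in SAP 3.4.1. Keep the existing rule for by-visit means and changes.

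The cost is SAP wording and a few extra table shells. The retests and early-termination samples are already part of the protocol, so no new data are needed. Only the tabulation changes; no retest, interruption or stopping rule is affected.
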